3.3.2. Efficacy Endpoints

The efficacy endpoints as measured at 26 weeks of weekly TransCon hGH treatment include the following:

- Annualized HV
- Δ HSDS
- Proportion of subjects with IGF-1 SDS of 0 to +2.0. Additionally, cut points of -2.0 to +2.0 and -1.0 to +2.0 will be assessed
- IGF-1 SDS
- IGFBP-3 SDS

3.3.3. C_{max}/Pharmacodynamic Endpoints

- Expected C_{max} of hGH in subjects <3 years old
- Serum IGF-1 SDS at 1-2 days post-dose in subjects <3 years old
- Serum IGF-1 SDS at 5 days \pm 1 day post-dose in all subjects

3.3.4. Other Endpoints

- Preference for TransCon hGH or commercially available daily hGH treatment
- Satisfaction with treatments for GHD: daily hGH and weekly TransCon hGH
- Impact of taking treatments for GHD: daily hGH and weekly TransCon hGH

4. ANALYSIS AND REPORTING

4.1. INTERIM ANALYSIS

No interim analysis is planned. An independent safety monitoring committee (ISC) will be established to monitor subject safety. Data used for ISC meetings will be handled according to the ICH E9 guidelines and therefore will not affect the study design and conduct from an efficacy perspective.

4.2. FINAL ANALYSIS

All final, planned analyses identified in this SAP will be performed after the last subject has completed the last study visit and end of study assessments, and all relevant study data have been processed and integrated into the analysis database.

5. GENERAL STATISTICAL CONSIDERATIONS

Descriptive summaries will be provided where appropriate for each of the primary and secondary variables.

Continuous, quantitative (absolute values at each time point and change from baseline if applicable) variable summaries will include the number of subjects (N) with non-missing values, mean, standard deviation (SD), standard error (SE), median, minimum, and maximum, unless otherwise specified.

Categorical, qualitative, variable summaries will include the frequency and percentage of subjects who are in the particular category. In general, the denominator for the percentage calculation will be based upon the total number of subjects in the study population for the cohorts, unless otherwise specified.

All data collected on eCRF will be presented in listings.

All analysis will be performed using SAS® Software version 9.4 or later.

5.1. BASELINE DATA

Baseline will be defined as the most recent non-missing assessment (including repeated and unscheduled assessments) before the study drug administration.

5.2. HANDLING OF MISSING DATA

In general, the observed data will be presented in listings. Imputed data will be used for summary or modeling analysis.

For the prior daily hGH treatment, if the day of first daily hGH treatment is missing, then impute the day to the 1st of that month. If both day and month are missing, then impute to Jan 1 of the year (eg, Jan 1, 2018). The duration will then be derived from the imputed date.

For Analysis of Covariance (ANCOVA) modeling, the following imputation will be done for the missing covariates:

- For subjects missing height data for one of the two parents, the average parental height SDS will be estimated based on the non-missing parental height SDS. For subjects with no parental height data, the population median parental height SDS from all subjects with parental height data will be imputed.
- If growth hormone stimulation data is missing at diagnosis, a value of 5 ng/mL will be used by convention.
- If subject took prior hGH treatment, but dose or duration is missing, the mean dose level will be used. If the prior hGH treatment date is completely missing and can't be imputed based on the rules stated before, the mean duration will be used for ANCOVA analysis.

For medication with missing start or end date, the following rules will be used to determine if it is prior or concomitant medication.

- If the start date is completely missing, but the end date is available and it is before the first dose date, then it will be counted as prior medication. Otherwise, it will be counted as both prior and concomitant medication.
- If both the start date and end date are completely missing, and it is ongoing, it will be counted as both prior and concomitant medication.
- If the start or end day is partially missing, Day 1 of the month will be used to determine if it is prior or concomitant medication. If both day and month of start date are missing, Jan 1 will be used to determine if it is prior or concomitant medication.

For determination of treatment-emergent adverse event (TEAE), if the start date and time of an AE are partially or completely missing, the AE will be assumed to be treatment-emergent if it cannot be definitely shown that the AE did not occur or worsen during the treatment-emergent period (worst case approach). The following rules are used for TEAE determination where the AE has a missing start date.

- If the start time of an AE is missing, but the start date is complete, an AE will only be excluded from treatment-emergent AEs if the start day is before day of first treatment or the start day is after end of study day.
- If the start time and day are missing but the start month is complete, an AE will only be excluded from treatment emergent AEs if the start month is before month of first treatment or the start month is after end month of end of study month or if the stop date/time is before the start of first treatment.
- If the start day and months are missing but the start year is complete, an AE will only be excluded from treatment-emergent AEs if the start year is before year of first treatment or if the start year is after end of study year or if the stop date/time is before the start of first treatment.
- If the start date is completely missing, an AE will not be excluded from treatment emergent AEs unless the stop date/time is before the start of first treatment.

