8.1 Trial Entry Criteria

8.1.1 Inclusion Criteria

- 1) Investigator-determined GHD diagnosis together with at least one of the following prior to the historical initiation of daily hGH therapy:
 - a. 2 GH stimulation test(s) with peak GH level of ≤ 10 ng/mL
 - b. Impaired height defined as at least one of the following:
 - i) ≥ 2 SD below the mean height for chronological age and sex when compared to the relevant growth charts:
 - (1) 2006 WHO Child Growth Standards for < 2 years old

- (2) 2000 CDC Growth Charts for the United States for ≥ 2 years old
 - ii) ≥ 1.5 SDS below mid-parental height
 - c. IGF-1 level ≥ 1 SD below the mean IGF-1 level standardized for age and sex according to the local laboratory reference values
 - d. Bone age x-ray ≥ 6 months less than chronological age
 - e. Diagnosis of at least one additional pituitary hormone deficiency
 - f. Congenital hypopituitarism due to congenital hypothalamic-pituitary defect (eg, ectopic posterior pituitary, pituitary hypoplasia, abnormal stalk, septo-optic dysplasia) or genetic defect (eg, GH1, POU1F1, or PROP1)
- 2) 6 months to 17 years old, inclusive, at Visit 1
 - a. If 3 to 17 years old, are taking daily hGH at a dose of ≥ 0.20 mg hGH/kg/week for at least 13 weeks but no more than 130 weeks prior to Visit 1
 - b. If ≥ 6 months but < 3 years old, are either hGH treatment-naïve or are taking daily hGH at a dose of ≥ 0.20 mg hGH/kg/week for no more than 130 weeks prior to Visit 1
- 3) Tanner stage < 5 at Visit 1
- 4) Open epiphyses (bone age ≤ 14.0 years for females or ≤ 16.0 years for males)
- 5) Written, signed, informed consent of the parent or legal guardian of the subject and written assent of the subject as required by the IRB/HREC/IEC

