9. EFFICACY ANALYSES

9.1. ANNUALIZED HV

Annualized height velocity is calculated based on the rules stated in [Section 5.4](#). An ANCOVA will be used to analyze by visit annualized height velocity. The model will include baseline age, peak GH levels (log transformed) at diagnosis, delta mid-parental height SDS, prior GH dose level (log transformed), and duration (log transformed) as covariates, and gender as a factor.

Summary tables including data and listings will be presented for all height measured during the trial.

9.2. ΔHSDS

Height Standard Deviation Score (HSDS) is derived based on the rules stated in [Section 5.4](#). The by visit change from baseline of the HSDS will be analyzed by ANCOVA model including baseline age, peak GH (log transformed) at diagnosis, delta mid-parental height SDS, prior GH dose level (log transformed), and duration (log transformed) as covariates, and gender as a factor.

Summary tables and Figures will be provided for HSDS and change from baseline in HSDS at each time point. Listings will also be generated for all the HSDS information.

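### A partly missing prior-hGH start date is set to the earliest date it could be, so derived prior duration is never understated and can exceed the 130-week entry limit or begin before the child's birth

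*SAP*

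**What the plan says.** SAP 5.2 has two rules for a partial start date of prior daily hGH. For a missing day: "if the day of first daily hGH treatment is missing, then impute the day to the 1st of that month". For a missing day and month: "If both day and month are missing, then impute to Jan 1 of the year (eg, Jan 1, 2018"). It continues: "The duration will then be derived from the imputed date". No floor or ceiling is stated.

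The same section says of imputed values in general: "Imputed data will be used for summary or modeling analysis". The mean-duration fallback is reserved for a date with no usable part: "If the prior hGH treatment date is completely missing and can't be imputed based on the rules stated before, the mean duration will be used". It does not reach a partial date.

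The derived duration is used in two places. SAP 7.1 summarises it as a baseline characteristic. SAP 9.1 enters it in the height-velocity ANCOVA, with "prior GH dose level (log transformed), and duration (log transformed) as covariates, and gender as a factor", and SAP 9.2 and 9.3 use it in the same form for change in height SDS, IGF-1 SDS and IGFBP-3 SDS.

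Two facts that could bound the imputation are known. Protocol 8.1.1 requires children aged 3 to 17 to have taken daily hGH "for at least 13 weeks but no more than 130 weeks prior to Visit 1"; treated children under 3 have the same upper limit and no minimum. SAP 5.4 states that birth date is collected on the eCRF.

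A neighbouring bullet in SAP 5.2 reads: "If subject took prior hGH treatment, but dose or duration is missing, the mean dose level will be used".

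**The concern.** Both date rules choose the first day of the recorded period, so errors cannot cancel: each one is zero or lengthens prior treatment. Elsewhere in SAP 5.2, first-of-period imputation only sorts medications into prior or concomitant, and the adverse-event rule is labelled a worst-case approach. Prior hGH duration is a number to be averaged and modelled, and an early date protects nothing there.

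Because the rule uses neither birth date nor the entry limits, it can produce values the trial's own data rule out. A baseline maximum above 130 weeks would look like an eligibility breach, and a child treated for longer than its life would look like a data error. In the models, imputed records would sit systematically to the right of exactly dated ones on the log-duration axis.

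**Working it through.** The plan gives no figure on this point to reproduce. The inputs are the two SAP 5.2 rules and the Protocol 8.1.1 limits (13 weeks = 91 days; 130 weeks = 910 days).

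**1. Size and sign of the error.** Overstatement = true start date − imputed start date. Over the 365 days of a non-leap year:

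| Missing part | Range | Mean | Share with zero error |
|---|---|---|---|
| Day | 0 to 30 days (4.3 weeks) | 14.7 days | 3.3% |
| Day and month | 0 to 364 days (52 weeks) | 182 days = 26 weeks | 0.3% |

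The means assume starts spread evenly over the year. The sign needs no assumption.

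**2. When 130 weeks can be passed.** The true duration must exceed 130 − 52 = 78 weeks for a year-only date, or 130 − 4.3 = 125.7 weeks for a missing day.

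**3. Worked dates, Visit 1 on 1 December 2017.**
- True start 1 December 2015, recorded as 2015. True duration: 731/7 = 104.4 weeks. Imputed from 1 January 2015: 1065/7 = 152.1 weeks.
- Child born 1 June 2016, start recorded as 2016. Age at Visit 1: 548/7 = 78.3 weeks. Imputed from 1 January 2016: 700/7 = 100.0 weeks on hGH, beginning 152 days before birth.

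A start before birth requires hGH start and birth in the same recorded year (or the same month, for a missing day). Given the 130-week limit, that confines it to children below about 1 + 910/365.25 = 3.5 years at Visit 1, an age range the trial enrols.

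**4. Log scale.** A true start of 25 December 2017 with Visit 1 on 26 March 2018 is 91/7 = 13.0 weeks. Recorded as 2017, it becomes 449/7 = 64.1 weeks, about 4.9-fold.

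**5. Illustrative frequencies.** These rest on assumptions, since the documents give no distributions: true duration uniform over 13 to 130 weeks and Visit 1 uniform over September 2017 to August 2018 (400,000 simulated records).
- Year-only records: mean overstatement 26.0 weeks; geometric mean ratio 1.45; 22% above 130 weeks (26% if Visit 1 falls in September 2017 to February 2018).
- Day-missing records: 1.8% above 130 weeks.
- Year-only records in treated children under 3: 27% to 30% start before birth, further assuming age uniform over 0.5 to 3 years and hGH started no earlier than 60 days of age.

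These are shares of partial records, not of subjects.

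**6. Bounded midpoint, year-only records, same assumptions, entry limits applied.** Mean error falls from 26.0 weeks to about 0, mean absolute error from 26.0 to 11.1 weeks and root-mean-square error from 30 to 13 weeks. None exceeds 130 weeks, by construction. The first child in step 3 would get the midpoint of 5 June to 31 December 2015, which is 115.1 weeks against a true 104.4.

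**7. Effect on the reported mean.** If 1%, 5% or 10% of treated subjects had year-only dates (assumed), mean duration would rise by about 0.01 × 26 = 0.3, 0.05 × 26 = 1.3 or 0.10 × 26 = 2.6 weeks.

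**The case against.** First-of-month and 1 January are familiar, transparent, pre-specified conventions, and SAP 5.2 also uses them for medication dates. Start date is an eCRF field (Protocol 9.9.1.1), and investigators review screening data for eligibility before Visit 1 (Protocol 10.2.2.1). A year-only date that imputes above 130 weeks cannot by itself show that the limit was met, so it should draw a query. Partial dates may therefore be rare and mostly lack only the day, which adds about two weeks. The primary objective is safety, efficacy is single-arm with no stated hypothesis test, and unadjusted summaries are also planned.

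All of this stands as an argument about size. It does not make the rule right: the sponsor foresaw partial dates, and the rule as written yields one-sided and sometimes impossible values.

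A second objection concerns the remedy. Forcing every imputed date into 13 to 130 weeks presumes eligibility and could hide a true deviation. This also stands, and the fix allows for it.

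Stronger readings are tempting but not supported:
- That duration is always overstated. The error is zero when the true start was the 1st of the month or 1 January.
- That children become ineligible. Eligibility is decided before Visit 1, and the Full Analysis Set (SAP 5.5) depends on dosing and follow-up, so nobody is excluded.
- That the rule defeats an adjustment for waning catch-up growth. SAP 9.1 gives no rationale for the covariate. If all dates were year-only, the log-scale correlation with the truth under the assumptions above would be 0.89 with the SAP rule and 0.90 with the midpoint. The gain lies in removing bias and impossible values.
- That recorded doses are overwritten. The dose bullet literally covers a missing duration, but its lead-in limits it to missing covariates and the next sentence deals with missing duration. It is loosely worded, no more.

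**Conclusion.** The point holds as a minor one. Followed exactly, SAP 5.2 never understates prior hGH duration and overstates it unless the true start was the imputed date. The error is bounded by calendar arithmetic: at most 30 days for a missing day and 52 weeks for a missing day and month. Durations above 130 weeks and starts before birth are possible outcomes of the rule.

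How often they would occur cannot be determined, because the documents do not give the share of partial dates. The 22% and 27% to 30% figures are conditional on year-only records and on the stated uniform assumptions. What is affected is a baseline summary and a covariate in the secondary efficacy models. Adjusted means in this single-arm trial should move little, and no safety conclusion depends on the value.

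**What to change.** Replace the partial-date rule in SAP 5.2 with:

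- Impute the midpoint of the recorded month or year after truncating it to dates not before birth and before Visit 1.
- Truncate it also to 13 to 130 weeks before Visit 1 (at most 130 weeks if under 3), unless a deviation on prior hGH duration is recorded for that subject. The exception keeps a true deviation visible.

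Reword the dose bullet so that a missing dose takes the mean dose, a missing duration takes the mean duration, and recorded values are kept.

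The cost is a few sentences in SAP 5.2 and a small change to one derivation before analysis. Birth date and Visit 1 date are already collected, and recorded deviations are already to be reviewed before database lock (SAP 6.2), so no new data are needed.

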12.1.3 Reporting Procedures for All Adverse Events

At each visit, all AEs will be documented in response to a general question about the subject's well-being and whether any possible changes in well-being have occurred since the previous visit. Additionally, at each visit, site staff will review subject diary data with the subject and parent/legal guardian/caregiver, to determine if diary entries reflect any AEs. There will be no direct questioning to solicit possible AEs.

AEs, including SAEs, will be documented through the end of the trial (ie, Visit 3). All AEs ongoing at Visit 3 or Early Termination Visit must be followed until the event is resolved or deemed stable by the investigator. All AEs must be recorded on the appropriate eCRF. AEs either observed by the investigator or reported by the subject must be recorded regardless of causality.

The following attributes must be documented for each AE:

- Subject ID
- Description
- Onset date (if AE was present on Day 1, include whether onset was prior to or after first dose of study drug)
- Resolution date, if applicable
- Severity
- Causality (relationship to study drug)
- Outcome
- Action taken
- Determination of “serious” (or not)

Any medical conditions, signs, symptoms, or illnesses active during the Screening Period (ie, up to approximately 4 weeks prior to first study drug administration) will be captured as medical history unless the change is trial procedure-related, in which case it will be reported as a non-treatment-emergent AE. Any changes to the conditions documented as medical history during the trial and that meet the above AE definition should be recorded as AEs so that a complete safety profile of the study drug is obtained. See [Section 12.2.2](#) for additional reporting procedures for serious AEs.

Any change from baseline health status that meets the above AE definition and occurs from the time of the first administration of study drug until end of Visit 3 or the Early Termination Visit will be recorded as an AE.

Abnormal laboratory values or test results constitute AEs if they:

- Induce a diagnosis, clinical sign(s), or symptom(s), or
- Are considered clinically significant by the investigator, or
- Require therapy.

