8.1. ADVERSE EVENTS

AE is defined as any untoward medical occurrence in a clinical investigation subject administered a pharmaceutical product and which does not necessarily have a causal relationship with the treatment. An AE can therefore be any unfavorable and unintended sign (including abnormal laboratory finding), symptom, or disease temporally associated with the use of a medicinal (investigational) product, whether or not related to that product. An AE can arise with any use (eg, in combination with another drug), route of administration, formulation, or dose, including an overdose.

An AE is considered treatment emergent, ie, Treatment Emergent Adverse Event (TEAE), is any AE that was first occurred or worsened after the first study dose and before the end of study. If the AE has any missing start date, the rules stated in [Section 5.2](#) will be applied to determine if it is treatment-emergent.

A serious AE (SAE) is SAE is any untoward medical occurrence that:

- Results in death
- Is life-threatening
- Requires inpatient hospitalization or prolongation of an existing hospitalization
- Results in persistent or significant disability/incapacity
- Is a congenital anomaly/birth defect

Summaries of incidence rates (frequencies and percentages) of individual TEAEs by MedDRA SOC and preferred term will be prepared. Such summaries will be displayed for all TEAEs, TEAEs by maximum intensity, and TEAEs by strongest relationship to study drug. In addition, related TEAE, non-related TEAE, TEAE leading to study drug discontinuation, and serious TEAE, by SOC, the preferred term and TEAE by preferred term will be also summarized. Especially, related includes definite, probable and possible relationship. Not-related includes unlikely/remote and unrelated/not related.

Each subject will be counted only once within each preferred term. If a subject experience more than one TEAE within a preferred term, only the TEAE with the strongest relationship or the maximum intensity, as appropriate, will be included in the summaries of relationship and intensity.

Data listing of AEs, TEAE leading to study drug discontinuation, serious TEAE will also be provided.

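### SAP 5.2 counts an untimed Day 1 adverse event as treatment-emergent even when it is recorded as having started before the first dose

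*SAP*

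**What the plan says.** SAP 5.2 introduces its TEAE date rules with a worst-case principle. An AE with a partly or wholly missing start date and time is assumed treatment-emergent "if it cannot be definitely shown that the AE did not occur or worsen during the treatment-emergent period". Four bullets follow. The first applies "If the start time of an AE is missing, but the start date is complete". In that case "an AE will only be excluded from treatment-emergent AEs if the start day is before day of first treatment", or if it falls after the end-of-study day. The other three bullets cover a missing day, a missing day and month, and a wholly missing date. Each of them also excludes an AE whose stop date/time precedes first treatment. The first bullet does not.

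SAP 8.1 gives the general definition: a TEAE "is any AE that was first occurred or worsened after the first study dose" and before the end of study. It sends AEs with a missing start date to the 5.2 rules, and 5.2 extends those rules to a missing start time.

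Protocol 12.1.3 lists what must be documented for each AE. The onset-date item carries an instruction: "if AE was present on Day 1, include whether onset was prior to or after first dose of study drug". The list names no clock time. The same section sends conditions active in Screening to medical history unless the change is related to a trial procedure, "in which case it will be reported as a non-treatment-emergent AE".

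**The concern.** The protocol requires the one piece of information that orders a Day 1 event relative to dosing, and the SAP rule for untimed events does not consult it. The word *only* in the bullet leaves a programmer no room to do so. The SAP then gives two answers for the same record: TEAE under the bullet, and not a TEAE under both the lead-in and SAP 8.1.

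The primary objective is safety and tolerability, and TEAE incidence is a main output for it. The trial has a single arm, so an event from before the first dose cannot be balanced against a control group. Protocol 5.4 describes the purpose as assessing the safety of switching from daily hGH, and Protocol 9.9.1.1 has treated children take their daily hGH the evening before Visit 1. A pre-dose Day 1 event therefore belongs to the period before the switch.

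**Working it through.** **The plan's own AE figure.** SAP 3.2 claims at least 95% probability of observing AEs with 2% incidence in 150 subjects, and with 1% incidence in about 300. Check: 1 − 0.98^150 = 0.952 and 1 − 0.99^300 = 0.951. Both hold. Neither is an input to this point, which concerns classification.

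**Classification of an AE with a complete Day 1 start date** (new onset, no later worsening):

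| Start time | Before/after entry | First bullet of SAP 5.2, read literally | SAP 8.1 and the 5.2 lead-in |
|---|---|---|---|
| Recorded, pre-dose | any | Does not apply | Not a TEAE |
| Recorded, post-dose | any | Does not apply | TEAE |
| Missing | after | TEAE | TEAE |
| Missing | blank | TEAE | TEAE (worst case) |
| Missing | before | **TEAE** | **Not a TEAE** |

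Only the last row gives conflicting answers. There the before-dose entry does show definitely that onset was not in the treatment-emergent period, so the lead-in's own test for exclusion is met.

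**Stop date.** Take an AE that began on Day 1 and ended before the dose. If the start day is missing but the month is known, the second bullet excludes it on its stop date/time. If the start date is complete and only the time is missing, the first bullet counts it. The better-dated record is classified less accurately, which looks like a drafting gap rather than a deliberate worst-case choice.

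**Which records can reach the last row.** Protocol 12.1.3 sends conditions active in Screening to medical history, and records changes from baseline as AEs from the first administration onward. What remains is mainly procedure-related events on the morning of Visit 1. Protocol 10.2.2.1 lists the assessments at that visit before dosing: questionnaires, vital signs, height and weight, a limited physical examination and Tanner staging. The Schedule of Events shows no blood draw or fundoscopy at Visit 1.

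**Size per record.** One misclassified child adds 1/N to the incidence of a preferred term. With N = 150 this is 1/150 = 0.0067, or 0.67 percentage points. The under-3 cohort has no fixed size, so N may differ; a larger N makes the step smaller.

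**The case against.** The strongest case against has four parts.

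- **The rule is conditional.** It applies only when the start time is missing. A Day 1 AE with a recorded pre-dose time falls under SAP 8.1 and is not a TEAE. The SAP states that the CRFs were reviewed, and it refers to start times and stop date/times, which suggests that times may be collected. This stands. A reader might infer that every fully dated Day 1 AE becomes a TEAE, because the protocol's attribute list names no onset time. That would be true only if the eCRF collects no start time, and the eCRF is not among the documents.
- **Few records qualify.** Most pre-dose conditions are medical history, and Visit 1 has few pre-dose procedures. This also stands and limits the size. It does not empty the set: the before/after entry is an attribute of AE records, so the protocol itself allows for AEs with pre-dose Day 1 onset.
- **The lead-in already permits exclusion.** This stands in part. The lead-in and SAP 8.1 support the right answer, so the fault is an internal inconsistency and not a clear intention to report known pre-dose events as TEAEs. But the bullets are the operative rules, and the first one says *only*.
- **The error is conservative.** It over-counts, it cannot hide a safety signal, and AEs are also listed individually. This is correct. Even so, the worst-case approach is meant for unknown timing, and here the timing is known.

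**Conclusion.** The point holds in a limited form. Under the first TEAE bullet of SAP 5.2, an untimed Day 1 AE recorded as starting before the first dose is counted as a TEAE, against SAP 8.1, the lead-in of SAP 5.2 and Protocol 12.1.3. The same bullet lacks the stop-date exclusion that the other three have.

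The effect is probably small. It always raises TEAE counts, by 0.67 percentage points in a preferred term per affected child if N = 150. The number of affected children cannot be derived from the documents.

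A reader might go on to infer that three such children (3/150 = 2.0%) would create an apparent incidence at the level the trial is sized for. The documents do not support this. Nothing suggests three such records sharing one preferred term, and the 2% in SAP 3.2 is a true incidence at which at least one event is likely to be seen, not a threshold for interpreting an observed rate.

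The conclusion rests on a literal reading of the bullet and on some Day 1 AE records having no start time.

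**What to change.** Keep the first bullet of SAP 5.2 and add to its exclusions: *or if onset is on Day 1 and is recorded as preceding the first dose, or the stop date/time precedes the first dose, in either case with no later worsening*. The clause should be added to the bullet and not replace it, because replacement would delete the exclusions for start days before first treatment and after end of study.

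A blank before/after entry stays treatment-emergent, in line with the worst-case approach. A later worsening is recorded as a new AE under Protocol 12.1.3 and is counted on its own date, so no true TEAE is lost.

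The cost is one clause in the SAP and a small change to the derivation code. The protocol already requires the information. Because the eCRF is not available here, the sponsor should confirm how the before/after entry is captured and that it reaches the analysis dataset.
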